13.2.2 Analysis of Secondary Endpoints

The secondary endpoints include the following:

13.2.2.1 Changes in the degree of pain-related functional interference measured by the BPI-SF interference score.

13.2.2.2 This trial will use change in average pain severity as an outcome measure based on recommendations from the initiative on Methods, Measurement, and Pain Assessment in Clinical Trials (IMPACT) and other CIPN or pain studies (16). Specifically, a previously published study investigating the effects of transdermal nicotine transdermal patches on post-operative pain observed an average of 1 point reduction in numerical pain scores in the nicotine group ([28](#)). Patient BPI-SF scores at baseline, during treatments, and post- treatment will be analyzed by a one-sided test of the hypothesis using a matched paired t-test. Nicotine transdermal patch safety and tolerability in non-smokers will be assessed using CTCAE v5.0 and PROs related to nausea, dizziness, vomiting, minor skin irritations, and palpitations.

Incidence and severity of AEs will be listed and summary descriptive statistics will be calculated.

13.3 Qualifying Toxicities for Early Stopping Rule

Early stopping criteria based on nicotine-related toxicities listed below will be used to ensure patient safety and tolerability. The stopping rule is based on a 30% maximum rate of toxic events. For all the toxic events the assumed null proportion of subjects with any dose-limiting toxicity is 30% for each of the 6 toxicities listed below.

The following toxic event as defined per CTCAE v5.0 will be counted toward the stopping rules in [Table 5](#).

- Grade 3 nausea
- Grade 3 vomiting
- Grade 3 dizziness
- Grade 3 pruritus
- Grade 3 headache
- Grade 2 heart palpitations

Table 5. Number of Subjects With Observed Toxic Events Needed to Stop Trial Given Accrued Sample Size.

Accrued Sample Size	Patient Number								
	10	15	20	25	30	35	40	45	50
Toxic Event Stopping Rule	6	8	10	12	14	16	18	20	21

13.4 Evaluability for Qualifying Toxicity and Efficacy

13.4.1 Qualifying Toxicity Evaluability

A patient is evaluable for nicotine-related toxicity if the patient has received any study treatment.

13.4.2 Efficacy Evaluability

All blood samples collected for an individual patient will need to be analyzed for serum nicotine levels to determine if an individual patient is evaluable for efficacy. A nicotine serum value of > 2.0 ng/mL and a cotinine serum value of > 2.0-20 ng/mL via LC-MS/MS analysis is consistent with the use of nicotine. A nicotine or cotinine serum value of > 10-20 ng/mL via immunoassay analysis is consistent with the use of nicotine. Evaluability may not be determined until the patient has completed the study treatment and is off study and serum nicotine analysis has been for all blood samples.

A patient is evaluable for efficacy if **ALL** of the following study requirements have been fulfilled:

- Attended at least 60% of the visits (≥ 3 out of 5 visits).
- Maintained a therapeutic level of serum nicotine for at least 60% of the serum nicotine analysis time points (≥ 3 out of 5 blood samples).
- Completed at least 60% of the survey/questionnaire data collection points (≥ 3 out of 5 data collection points; and 2 out of 4 for the PGIC). Each data collection point will include an EORTC QLQ-CIPN-20 questionnaire and BPI-SF questionnaire. The neuropathy upper and lower extremity PGIC questionnaires will only be collected at 4 points throughout the study.

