1.2.1 Preclinical Data

Paclitaxel and cisplatin have been shown to produce a long-lasting, bilateral neuropathy in mice, featuring hypersensitivity to mechanical and cold stimuli (14). Consequently, well-established mouse models of CIPN have been used by our group (15), as well as other laboratories to investigate nAChRs as potential targets for amelioration and/or prevention of CIPN. In a dose-dependent manner, nicotine has been shown to reverse the mechanical and cold allodynia induced in rats treated with oxaliplatin (9) and in mice treated with paclitaxel (Figure 1) (16). The doses of nicotine used generated plasma concentrations (20 to 30 ng/ml at doses of 0.6 and 0.9 mg/kg) of the drug, well within the concentration range of nicotine reported for nicotine transdermal patches users. These results strongly support the potential utility of nicotine in mitigating CIPN.

[figure not shown]

Figure 1. Nicotine reverses paclitaxel-induced mechanical allodynia in mice.

Male C57BL/6J mice received 8 mg/kg paclitaxel via intraperitoneal (i.p.) injection every other day for a total of 4 injections. At 2 weeks post-paclitaxel injections, mice received a single i.p. injection of saline or nicotine. Mechanical threshold was determined via von Frey filament testing on the left and right hind paws. Error bars represent the standard error of the mean for one experiment ($n = 6$). A two-way ANOVA revealed significant differences; * $p < 0.05$ vs saline. BL, baseline.

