11 SERUM NICOTINE ANALYSIS

11.1 Participation in Serum Nicotine Analysis

A blood sample collected for the analysis of serum nicotine levels will be used to confirm that patients meet eligibility and screening criteria. Blood samples will also be collected once during Cycle 1, once at the beginning of Cycle 2 before nicotine transdermal patch administration, once during Cycle 2, and once during the 30-day follow-up period to measure serum nicotine levels throughout the study (a total of 5 blood samples). Participation in serum nicotine studies using blood samples is mandatory.

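### Section 13.4.2 makes efficacy evaluability depend on a therapeutic serum nicotine level that is given no value, and it conflicts with the all-patients rule in section 13.1

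*Combined protocol and SAP*

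**What the plan says.** Section 13.4.2 requires every serum sample to be analysed before a patient is classed as evaluable for efficacy. Three conditions must all hold: attendance ("Attended at least 60% of the visits (≥ 3 out of 5 visits"), a matching questionnaire-completion rule, and an exposure rule: "Maintained a therapeutic level of serum nicotine for at least 60% of the serum nicotine analysis time points (≥ 3 out of 5 blood samples".

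The section attaches no ng/mL value to that level. The figures it does give describe detection of nicotine use:

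- LC-MS/MS: nicotine above 2.0 ng/mL and "a cotinine serum value of > 2.0-20 ng/mL via LC-MS/MS analysis is consistent with the use of nicotine". The nicotine limit is a single value, the cotinine limit is a range, and the two are joined by AND.
- Immunoassay: "A nicotine or cotinine serum value of > 10-20 ng/mL via immunoassay analysis is consistent with the use of nicotine". The limit is a range, and the analytes are joined by OR.

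It adds that the decision may have to wait until the patient has finished treatment and is off study.

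Elsewhere:

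- Section 13.1 (Sample Size and Accrual) calls a patient evaluable when pain scores exist at each dose level, and puts all patients in the final analysis, with imputation.
- Section 13.2.1 specifies a one-sided paired t-test and names no analysis set.
- Section 11.2.1 lists the five draws: screening, Cycle 1 Day 8, Cycle 2 before the patch, Cycle 2 Day 8, and follow-up.
- Section 11.2.2 refers to the laboratory's specimen specifications. No section says which assay will be used.
- Section 11.1 gives the serum test a second job: "A blood sample collected for the analysis of serum nicotine levels will be used to confirm that patients meet eligibility and screening criteria".

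**The concern.** A rule that decides who is evaluable must sort each sample the same way whoever applies it. This one has no number of its own. The detection limits that might stand in for it include two ranges and two different logics.

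Timing makes this more than untidy wording. The trial is open label (section 3.1), the biostatistician and study team review data at least quarterly (section 14.1), and serum status may be settled once a patient's scores are all in. An open threshold then leaves room to decide who counts with outcomes in view. Even with no such intent, selecting on a post-baseline serum result keeps the patients who tolerated and wore the patch, and their mean change need not represent everyone treated. The word evaluable also closes recruitment in section 13.1, so two meanings of it matter there as well.

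**Working it through.** **Planned size, for reference.** Inputs from section 13.1: effect size 0.54, 5% level, n = 47, 10% dropout. The implied SD of change is 2.7/0.54 = 5.0. Paired t-test power from the noncentral t (46 df, noncentrality 0.54 × √47 = 3.70) is 0.952 two-sided and 0.977 one-sided. 47 × 1.1 = 51.7, giving 52. The plan's figures reproduce, and this point does not disturb them.

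**Step 1. Can the printed limits classify a sample?**

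- Width: LC-MS/MS cotinine 20/2.0 = 10-fold; immunoassay 20/10 = 2-fold. The lowest nicotine limits of the two assays differ by 10/2.0 = 5-fold.
- Nicotine alone, as the exposure rule is worded: 5 ng/mL passes the LC-MS/MS limit and fails the immunoassay limit at either end. 15 ng/mL passes LC-MS/MS and sits inside the immunoassay range.
- Nicotine 5 with cotinine 8: by LC-MS/MS this passes if the cotinine limit is 2.0 and fails if it is 20. By immunoassay it fails either way.
- Nicotine below 2.0 with cotinine above 20: this fails LC-MS/MS (AND) and passes immunoassay (OR).

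So the classification depends on the assay, on the end of the range and on which analytes count.

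**Step 2. Does settling the number rescue the rule?** Two draws are on patch (detection probability p) and three are off patch (positive with probability q). Assuming independent draws,

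P(at least 3 of 5) = p²[1 − (1 − q)³] + 2p(1 − p)[3q²(1 − q) + q³] + (1 − p)²q³.

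With p = 1 and q = 0 this is 0: the maximum is 2 of 5, so 0 of 52 patients qualify at any cut-off. The documents give neither p nor q, so the range is by assumption, with p from 0.6 to 1.0:

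- q = 2%: 1.1 to 3.1 of 52
- q = 5%: 2.9 to 7.4 of 52
- q = 10%: 5.8 to 14.1 of 52

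For example, p = 1 and q = 0.05 gives 1 − 0.95³ = 0.1426, and 52 × 0.1426 = 7.4. A patient can qualify only if a sample drawn off patch reads positive.

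**Step 3. What if serum decided the primary set on the two on-patch draws?** Assume both must pass, independently, with the same per-draw pass rate r. Then 52r² patients remain. Power is one-sided at 5%, effect size 0.54, with the count rounded down:

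- r = 0.95: 46.9 remain, power 0.975
- r = 0.90: 42.1 remain, power 0.964
- r = 0.80: 33.3 remain, power 0.918
- r = 0.60: 18.7 remain, power 0.71

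**Step 4. The two sections side by side.** Section 13.1 sets no serum condition and includes everyone. Section 13.4.2 makes serum a necessary condition for efficacy evaluability. Neither refers to the other, and section 13.2.1 does not choose between them.

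**The case against.** The strongest reply is that section 13.1 already includes all patients, so serum status may never touch the primary analysis. That stands as far as it goes: the documents do not show that 13.4.2 governs the primary test. Equally, they do not say that it does not, and a section on efficacy evaluability naturally invites that use.

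The reply can add that the exposure rule speaks of nicotine, and LC-MS/MS nicotine has a single limit, so the cotinine range may be irrelevant. That is correct, and not every cut-off is a range. It helps only if LC-MS/MS is the assay and the use limit is the intended level, and neither is stated.

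Sections 9.1.1 to 9.1.8 are absent from the public text. A therapeutic value could sit there; if so, 13.4.2 should cite it.

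Four stronger readings are tempting and are not supported:

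- That 13.4.2 defines the use limits as the therapeutic level. It never equates them; the term is simply undefined.
- That the use limit is too low because section 1.2.1 reports doses that "generated plasma concentrations (20 to 30 ng/ml at doses of 0.6 and 0.9 mg/kg". Those are animal data and are not offered as a human threshold.
- That 7 mg samples are the most likely to be unclassifiable. Even if serum level were proportional to dose (an assumption), immunoassay nicotine of 15 at 14 mg would fall inside 10-20, while 7.5 at 7 mg would be clearly below it. Evaluability is also decided per patient, so an exclusion removes both doses.
- That screening is judged by the 13.4.2 limits. Section 11.1 does not refer to them; it leaves the screening cut-off unstated.

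**Conclusion.** The point holds in this form: the exposure criterion in 13.4.2 cannot be applied reproducibly as written, and its role conflicts with section 13.1. What is undetermined is who is evaluable for efficacy under 13.4.2 and whether that status matters to the primary test. The documents do not establish that the primary set itself hangs on the cut-off.

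The uncertainty in the limits is 10-fold for LC-MS/MS cotinine, 2-fold for immunoassay, and 5-fold between the assays' lowest nicotine limits. The count problem is separate and larger: a literal reading leaves 0 of 52 evaluable if off-patch samples are negative. That treats the follow-up draw as off patch; its 7-day allowance could bring it close to patch removal, and the documents give no elimination data. The pass rates and positivity rates above are assumptions. The change is worth making because it is cheap and closes a route to selection after outcomes are known.

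**What to change.** - In 13.2.1, state that the primary analysis follows section 13.1 (all patients, with its missing-data handling) and that serum status does not decide who enters it. Bring the definition of evaluable in 13.4.2 into line with 13.1, including for closing recruitment.
- Use serum only for a supportive exposure-confirmed analysis based on Cycle 1 Day 8 and Cycle 2 Day 8, in place of the 3-of-5 count.
- For that analysis, fix one assay, one cut-off per analyte and one AND/OR rule before any efficacy look.
- Describe the criterion as consistent with patch use, unless a therapeutic value and its source are given.
- State which cut-off applies to the screening sample in 11.1.

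The cost is protocol wording only, since the samples are already planned. The downside is that the primary set may include some poorly adherent patients, which slightly dilutes the effect; the supportive analysis gives a check on this.

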6.2 Investigational Agent Administration

6.2.1 Nicotine Transdermal Patch Administration and Treatment Schedule:

- Each patient will complete two 14-day treatment conditions, one each for 7 mg and 14 mg nicotine transdermal patch administration with a washout period in between (\geq 14 days and up to 21 days).
- Nicotine transdermal patch administration will begin on Cycle 1, Day 1 (7mg) and Cycle 2, Day 1 (14mg).
- Nicotine transdermal patches will be applied once daily for 14 consecutive days.
- Nicotine transdermal patches will be removed for at least 14 days and up to 21 days at the end of Cycle 1, Day 14.
- Patients will be instructed as follows:
 - Apply the nicotine transdermal patch to dry, clean, hairless skin
 - Patients should apply and remove the nicotine transdermal patch at the same time everyday
 - Patients should wear the nicotine transdermal patch for at least 16 hours per day.

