11.2.1 Collection Time Points

Blood samples will be collected at the following time points:

- Eligibility/Baseline (during eligibility screening)
- Cycle 1, Treatment Condition 1, Day 8 or within 5 days
- Cycle 2, Treatment Condition 2, before nicotine transdermal patch administration
- Cycle 2, Treatment Condition 2, Day 8 or within 5 days
- 30-day follow-up period, Day 8-15 or within 7 days

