12 STUDY CALENDAR

Table 3. Study Caledar – Eligibility/Screening Through Washout Period

	Eligibility and Screening	Cycle 1 Treatment Condition 1 7mg Nicotine Transdermal Patch ^A			Washout Period No Nicotine Transdermal Patch ^B
	Within 14 Days	D1	D2	D8 ^C	
Informed Consent ^D	X				
Demographics	X				
Vital Signs (BP, HR) ^E	X	X		X	
Baseline Conditions/Symptoms	X				
Medical/Surgical History	X				
Exam ^F	X ^G			X	
Concurrent Medications ^H	X	X		X	
Urine Pregnancy Test	X				
Serum Nicotine Level	X			X	
Assessment of AEs		X		X	
BPI-SF	X			X	
QLQ-CIPN 20	X			X	
PGIC Neuropathy (upper and lower)				X	
AE Assessment Phone Call			X		X ^I

Table 3 Footnotes:

- A. Each Treatment Condition Cycle is 14 days.
- B. Washout period may occur for \geq 14 days and up to 21 days after the removal of the nicotine transdermal patch on Cycle 1
- C. Cycle 1, Day 8 study visit may occur within 5 days.
- D. If registration is delayed to more than 14 days after the informed consent form is signed, a new signed consent form is not required unless the IRB has approved a newer version.
- E. Include ECOG performance status.
- F. Exam will also include a neurological exam: sensory, motor, reflex, Romberg, and gait.
- G. If the neurological exam cannot be completed on the day of screening, it can be completed on Cycle 1, Day 1, but does not need to be completed for both screening and Cycle, Day 1.
- H. Include over-the-counter medications.
- I. The AE assessment phone call during the washout period will include notation of the date the last nicotine transdermal patch was removed in Cycle 1.

Table 4. Study Calendar – Treatment Condition 2 Through the 90-Day Follow-up Period

	Cycle 2 Treatment Condition 2 14mg Nicotine Transdermal Patch ⁰			30-Day Follow-up Period		90-Day Follow-up Period ^B
	D1 ^C	D2	D8 ^D	D1	D8 - D15 ^E	
Vital Signs (BP, HR) ^F	X		X		X	
Exam ^G	X		X		X	
Concurrent Medications ^H	X		X		X	
Serum Nicotine Level	X ^I		X		X	
Assessment of AEs	X ^I		X		X	
BPI-SF	X ^I		X		X	
PGIC Neuropathy (upper and lower)	X ^I		X		X	
QLQ-CIPN 20	X ^I		X		X	
AE Assessment Phone Call		X		X ^J		
Follow-up Phone Call						X ^{B, K}

Table 4 Footnotes:

- A. Each Treatment Condition Cycle is 14 days.
- B. The 90-day follow-up period will begin at the end of Cycle 2, after the last nicotine transdermal patch is removed. The 90-day follow-up phone call may occur \pm 14 days.

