- C. Cycle 2, Day 1 may occur \geq 14 days and up to 21 days after the removal of the nicotine transdermal patch in Cycle 1.
- D. Cycle 2, Day 8 study visit may occur within 5 days.
- E. 30-day follow-up, Day 8 - Day 15 study visit may occur within 7 days.
- F. Include ECOG performance status.
- G. Exam will also include a neurological exam: sensory, motor, reflex, Romberg, and gait.
- H. Include over-the-counter medications.
- I. Must occur before 14 mg nicotine transdermal patch is administered.
- J. 30-day follow-up, the AE assessment phone call will include notation of the date the last nicotine transdermal patch was removed in Cycle 2.
- K. 90-day follow-up, the phone call will assess whether patients have continued to use the nicotine transdermal patch to lessen their CIPN symptoms and if they have developed a dependence to nicotine in any form (eg, cigarettes, electronic cigarettes, smokeless tobacco, or other nicotine-containing products).

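### Section 13.4.2 asks for a therapeutic nicotine level in 3 of 5 samples, but only 2 of the 5 draws fall in a patch period, so on-patch exposure alone cannot make a patient evaluable for efficacy

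*Combined protocol and SAP*

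**What the plan says.** Section 13.4.2 lists three requirements for efficacy evaluability, all of which must be met. The serum requirement reads "Maintained a therapeutic level of serum nicotine for at least 60% of the serum nicotine analysis time points", and the section gives the count as at least 3 of 5 samples.

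Sections 11.1 and 11.2.1 and the study calendar fix the five draws:

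- **Screening.** Section 11.1 states its purpose: "A blood sample collected for the analysis of serum nicotine levels will be used to confirm that patients meet eligibility and screening criteria".
- **Cycle 1 Day 8**, with a 5-day window, during the 7 mg condition.
- **Start of Cycle 2**, listed as "Cycle 2, Treatment Condition 2, before nicotine transdermal patch administration". Footnote I to Table 4 repeats the condition: "Must occur before 14 mg nicotine transdermal patch is administered". Section 6.2.1 sets the gap before it: "Nicotine transdermal patches will be removed for at least 14 days and up to 21 days at the end of Cycle 1, Day 14".
- **Cycle 2 Day 8**, with a 5-day window, during the 14 mg condition.
- **Follow-up**, listed as "30-day follow-up period, Day 8-15 or within 7 days", after the last patch.

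On cycle length, the calendar says: "Each Treatment Condition Cycle is 14 days". Criterion 4.1.3 requires 14 nicotine-free days before treatment, and 4.1.8 requires willingness to abstain from other nicotine through the 30-day follow-up.

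Section 13.4.2 does not say what level is therapeutic. It gives only values taken to indicate nicotine use: by LC-MS/MS, nicotine above 2.0 ng/mL and cotinine above 2.0-20 ng/mL; by immunoassay, nicotine or cotinine above 10-20 ng/mL.

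Section 13.1 (Sample Size and Accrual) has a different definition: a patient with pain scores at both doses is evaluable. It closes recruitment once enough evaluable patients have been obtained, and puts all patients in the final analysis, with a proviso about excessive missing values. Section 13.2.1 names no analysis set.

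**The concern.** The serum rule looks like a check that patients wore their patches, but its denominator includes three draws at which the schedule has no patch in place. A patient who does everything the protocol asks, and whose serum is positive only during patch periods, would fail it. To pass, a patient needs on-patch exposure plus either residual drug or off-protocol nicotine at a draw meant to be off patch.

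Two further gaps compound this. Cut-offs written as ranges let two analysts classify the same sample differently. And because 13.1 and 13.4.2 define evaluable differently, one patient can be evaluable under one section and not the other, while the end of recruitment depends on that word.

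**Working it through.** **The plan's own figure.** 0.60 × 5 = 3, so 60% and 3 of 5 agree with each other. The question is whether the schedule can supply three on-patch samples.

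**Classifying the draws** (11.2.1, 6.2.1, Tables 3 and 4).

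| Draw | Patch period? | Basis |
|---|---|---|
| Screening | No | Before any study patch |
| Cycle 1 Day 8 | Yes | 8 − 5 = Day 3 to 8 + 5 = Day 13 |
| Cycle 2 pre-patch | No | After 14 to 21 patch-free days |
| Cycle 2 Day 8 | Yes | Day 3 to Day 13 |
| Follow-up | No | After the last patch |

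The direction of the windows is not stated. Day 3 to 13 is the widest reading and an after-only reading gives Day 8 to 13. Both lie inside the 14-day cycle, so visit timing cannot turn an off-patch draw into a third on-patch one.

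**Maximum from on-patch exposure.** 2/5 = 40%, below 3/5 = 60%.

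**Enumerating the outcomes.** Call each sample positive or negative, taking positive to mean that it meets whatever level 13.4.2 intends. There are 2^5 = 32 patterns, and 16 have at least three positives. None of the 16 has all three off-patch samples negative.

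With screening negative, the passing patterns number C(4,3) + C(4,4) = 4 + 1 = 5:

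| Pattern | C1 Day 8 | C2 pre-patch | C2 Day 8 | Follow-up |
|---|---|---|---|---|
| 1 | + | + | + | − |
| 2 | + | − | + | + |
| 3 | + | + | − | + |
| 4 | − | + | + | + |
| 5 | + | + | + | + |

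- All 5 contain an off-patch positive.
- Patterns 1, 3, 4 and 5 (4 of 5) need it at the Cycle 2 pre-patch draw, after at least 14 days without a patch.
- Pattern 2 is the only other route and needs a positive follow-up sample.
- All 5 also contain at least one on-patch positive; patterns 1, 2 and 5 contain both.

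**Can the follow-up sample be positive?** At the widest reading its window runs from 8 − 7 = Day 1 to 15 + 7 = Day 22 of follow-up; on an after-only reading it starts at Day 8. Either can be shorter than the protocol's own 14-day minimum washout. The text available gives no basis for estimating how often a compliant patient would still be positive, so no yield is calculated.

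**The case against.** The best defence is that 13.1 governs. Its definition has no serum condition and it includes all patients in the final analysis, so the 13.4.2 set may never decide accrual or the primary test. That stands as one reading, and it limits how serious the point is. It does not repair 13.4.2, which on its own terms still cannot recognise a patient who is positive only on patch, and the plan does not say which section governs.

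A second defence is that the rule means the expected status at each draw, negative off patch and positive on patch. A fully adherent patient would then score 5 of 5. The wording does not support this: it counts samples with a therapeutic level.

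A third is that the public text moves from section 8.5 to 9.1.9, so a definition of the therapeutic level, or elimination data, may sit in sections not shown. That is fair, and statements here about either are limited to the text available. The count of two on-patch draws does not depend on them.

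Two stronger readings are tempting. A reader might infer that no patient can be evaluable, or that the trial cannot reach its required number. The documents do not show this, because a follow-up sample may still be positive and 13.1 may govern. A reader might also infer that the rule ignores adherence. It does not: every passing pattern with a negative screening sample includes an on-patch positive. The fault is that on-patch exposure is not enough.

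**Conclusion.** The contradiction between 13.4.2 and the sampling schedule is real and should be corrected. It rests on a count from the protocol's own calendar and needs no assumed rates. The pattern results assume only a negative screening sample, which is what eligibility calls for.

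The consequence depends on which section governs. Under 13.1, accrual and the primary test are not affected, and the harm is confined to an evaluability definition that does not do its job. Under 13.4.2, adherent patients who are positive only on patch are excluded, and those retained are selected on residual drug or off-protocol nicotine. How many would be lost cannot be sized from the text available. The range cut-offs and the two definitions of evaluable need settling in either case.

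**What to change.** In 13.4.2:

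- Apply the serum criterion only to the Cycle 1 Day 8 and Cycle 2 Day 8 samples. Since 1 of 2 is 50%, a 60% threshold means both positive.
- Use the screening, Cycle 2 pre-patch and follow-up samples only to check abstinence.
- Set one positivity cut-off per assay before analysis, in place of each range, and state whether the LC-MS/MS rule needs both nicotine and cotinine.
- Use the diary times (6.7) and sample collection times (11.2.3) to interpret a negative Day 8 result. Do not discard a positive result because the patch was off at the draw. Section 6.2.1 says "Patients should wear the nicotine transdermal patch for at least 16 hours per day", so a compliant patient may be without a patch for up to 24 − 16 = 8 hours.

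Reconcile 13.1 with 13.4.2 by stating which definition counts toward accrual and which set the primary test uses. Section 13.1 already includes all patients in the final analysis, subject to its proviso on missing values.

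**Cost.** A few sentences; no new samples, visits or patients. Requiring both Day 8 samples removes the tolerance for a missed one, so a patient with a missing or negative Day 8 sample leaves the 13.4.2 set. Let p be the chance that a Day 8 sample is drawn and positive, taken as independent between cycles. The values of p are assumptions. The number remaining is 52 × p². Power is for a one-sided 5% paired t-test at the plan's effect size of 0.54 (noncentral t, noncentrality 0.54 × √n).

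| p | 52 × p² | n | Power |
|---|---|---|---|
| 0.95 | 46.9 | 47 | 0.977 |
| 0.90 | 42.1 | 42 | 0.964 |
| 0.85 | 37.6 | 38 | 0.948 |

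The plan's 10% allowance for dropout or non-compliance is not deducted as well, because p already covers samples missed for those reasons. A primary analysis on all patients is unaffected.
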